
	
2c) Suvorexant will be well tolerated by the participants.
 
2d) Sleep latency and wake after sleep onset (WASO) will be reduced with suvorexant treatment compared with placebo.
 
2e) (exploratory hypothesis) When reduced at baseline (i.e. SWS below 100 minutes and mean REM segment duration below 15 minutes) SWS and the duration of continuous segments of REM sleep will increase with suvorexant compared with placebo.

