Orexin antagonists are a new class of therapeutic agents that are promising for diminishing arousal to maintain overall sleep and specifically REM sleep. Orexin is implicated in coordinating brain stem centers that initiate and maintain states of arousal and are deficient in narcolepsy, a disorder with excessive and disinhibited REM sleep.²¹ The Merck product suvorexant is a dual orexin receptor antagonist and the first and to date only FDA approved agent from this class.²¹ Results of the 2, pivotal 3 month trials involving over 2000 patients²² have been reported as well as a 1 year trial where 522 patients received suvorexant.²³ Suvorexant has shown consistent efficacy in reducing insomnia, and in reducing WASO and latency to persistent sleep in people with primary diagnoses of insomnia. It has also been well tolerated with somnolence being the most common adverse effect, endorsed by 7% of insomnia patients receiving approved doses versus 4% of those receiving placebo. Only 3% of trial participants receiving suvorexant discontinued treatment due to adverse effects which was comparable to the rate for those receiving placebo. Of note, despite targeting a system that is implicated in narcolepsy, there were no incidences of cataplexy observed in these clinical trials. Orexin antagonists have been shown to increase REM and SWS in animal models, however, in healthy humans (without disturbed sleep) there were no significant changes in the amount of REM sleep nor changes in the distribution of spectral EEG frequencies within each sleep stage.²¹ Based on

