--	--

Adverse Event Screening At each medication visit participants will be queried regarding the presence of any new symptoms or concerns. We will specifically query the adverse effects that occurred at a frequency that exceeded placebo in either the 3 month pivotal trials²² or the 1-year study²³ including somnolence, fatigue, dry mouth, dyspepsia, and peripheral edema. We will also specifically query the pre-specified events of interest for those trials including suicidal ideation, complex sleep-related behaviors (e.g. getting food during the night and not remembering it), sleep onset or off-set hallucinations, sleep paralysis, and falls. Excessive daytime sleepiness will be assessed by administering the Epworth Sleepiness Questionnaire.³¹ Weight and vital signs will be obtained at each study visit. At the post-treatment visit specific inquiry will also include the occurrence of common medication withdrawal symptoms such as dizziness, shaking, nausea, and muscle tension as well as re-assessment of insomnia and sleep patterns for that period.

Polysomnography (PSG):

PSG collection includes a standard electroencephalogram (EEG) montage with two central, frontal, and occipital leads, two electrooculograms, chin and limb electromyograms, and an electrocardiogram (ECG). Recordings will be conducted using an Embla (Denver, CO) Titanium unit in the CRU. Screening for sleep disordered breathing and limb movements will be performed using the screening night data. Visual scoring of sleep records from a computer monitor will be done following the American Academy of Sleep Medicine (AASM) Manual, Version 2.0.³² The REMLogic software (Embla) will calculate sleep parameters including TST, SOL, WASO, the percentage of each sleep stage, and mean duration of continuous REM segment. Calculation of REM segment length used our previous criteria¹⁶ of at least two epochs of consecutive REM sleep with no more than one 30-sec epoch of non-REM sleep interruption. The sleep parameters for baseline will be obtained from the second night recording after an accommodation recording that will also screen for apnea will be used in data analysis. Respiratory strain gauge, nasal air flow, and oximetry monitors will be included on the first but not subsequent nights. Participants will be instructed to go to bed near their habitual bedtimes and will wake up naturally. PSG will be done prior to medication and after 3 weeks of medication treatment to allow for stable dosing.

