2.7 Statistical Analysis and Sample Size Justification	
The data will be analyzed by the Investigator and Co-investigator.
 
Main outcomes will be ISI, CAPS nightmare frequency and total score, diary and PSG sleep latency and WASO at week 3 and for non-PSG variables Med week 6. We will also explore effects on REM and SWS and their relationships to other study outcomes.
 
An alpha level of .05 (one-tailed) will be applied in testing Hypotheses 2a), 2b), 2d), and 2e). Initially, data will be pre-screened for errors, outliers, normality of distributions, and any necessary modifications, such as transformation of variables and/or elimination of cases, will be conducted.
 
Our initial objectives are descriptive. We will generate frequencies of types of trauma exposures associated with insomnia and the rates for PTSD diagnoses and sub-diagnostic threshold PTSD symptoms in the recruited study population (Objective 1) and the frequency of adverse events (Objective 2). The latter will be descriptively contrasted to the extant data for suvorexant from the insomnia registry trials as a guide to planning future trials including dosing.
 
Hypothesis 2a) Insomnia will improve, and nightmares and other PTSD symptoms will be reduced with suvorexant treatment compared with placebo: We will compare baseline characteristics of the treatment groups using independent samples t-tests for continuous variables or chi-square tests for categorical variables. If a significant group difference is found in some of the variables, the variable(s) will be included in subsequent analyses as a covariate(s). We will perform 2 (Group) x 3 (Time: baseline, Med week 3, and week 6) mixed ANOVAs or ANCOVAs [if there is a covariate(s)] to compare the changes in ISI scores, nightmare frequency, and CAPS scores, separately, between the two groups.
 
Hypothesis 2b) Improved sleep will be associated with reduced non-sleep PTSD symptoms: Correlation coefficients between baseline – Med week 6 changes in sleep measures (e.g., ISI scores and nightmare frequency) and changes in the CAPS scores excluding two sleep-related items will be computed. In addition, we will exploratively examine if there is an interaction with treatment condition by performing regression analyses in which CAPS scores will be predicted by changes in sleep measures, treatment condition, and a Sleep measure X Treatment condition interaction.
 
Hypothesis 2d) Sleep latency and wake after sleep onset (WASO) will be reduced with suvorexant treatment compared with placebo: We will perform 2 (Group: suvorexant vs. placebo) x 2 (Time: Baseline and Med week 3) mixed ANOVAs or ANCOVAs [if there is a covariate(s)] to compare the changes in PSG measured sleep latency and WASO between the suvorexant and placebo groups.
 
Exploratory hypothesis 2e) When reduced at baseline (i.e., SWS below 100 minutes and mean REM segment duration below 15

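### Section 2.7 names only external trial data as the comparator for adverse events; no comparison with the trial's own randomised placebo arm is stated

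*Combined protocol and SAP*

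**What the plan says.** Hypothesis 2c in section 2.1 reads "Suvorexant will be well tolerated by the participants", with no criterion and no comparator. The narrative of section 2.1 and the Summary of Significance in section 2.2 both describe a placebo-controlled evaluation that includes tolerability, and section 2.5 (Medication) randomises participants to suvorexant or placebo.

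The adverse-event analysis is in section 2.7. Frequencies will be generated, and then: "The latter will be descriptively contrasted to the extant data for suvorexant from the insomnia registry trials". The stated purpose is to serve "as a guide to planning future trials including dosing". The text does not say whether frequencies will be shown by arm or pooled. The sentence on testing leaves 2c out: "An alpha level of .05 (one-tailed) will be applied in testing Hypotheses 2a), 2b), 2d), and 2e". Hypotheses 2a, 2b, 2d and 2e each have an analysis paragraph; 2c has none.

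On collection, section 2.5 (Adverse Event Screening) combines an open question with a prompted list: "We will specifically query the adverse effects that occurred at a frequency that exceeded placebo" in the earlier trials, plus those trials' pre-specified events of interest and the Epworth questionnaire. Section 2.2 gives the external benchmark for somnolence, "endorsed by 7% of insomnia patients receiving approved doses versus 4% of those receiving placebo".

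**The concern.** The trial pays for a randomised, blinded placebo group and questions it in the same way as the active group. The one safety contrast written into the analysis section nevertheless looks outside the trial. That contrast is not randomised, and the documents themselves show that the external trials differ from this one.

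If section 2.7 is followed as written and nothing is added, the answer to 2c rests on whether the suvorexant rates here look higher or lower than in trials of primary insomnia. A gap could come from the drug behaving differently in this population. It could equally come from different background symptoms, length of follow-up, dosing or questioning, and the external contrast cannot separate these. This matters because the result is meant to inform the design and dosing of later trials. The efficacy conclusions are not affected.

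**Working it through.** The plan gives no expected rate, sample size or alpha for adverse events, so there is no figure to reproduce. The check sets the two sources side by side and then asks what a within-trial comparison could deliver.

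**1. The two sources, from the documents.** Section 2.7 does not list which external trials it means; I take them to be the 3-month pivotal trials and the 1-year trial cited in sections 2.2 and 2.5.

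| Feature | External trials | This trial |
|---|---|---|
| Population | Primary insomnia (2.2), including elderly patients (2.7, power section) | Age 18-55, trauma-related insomnia, about half expected to have PTSD (2.5) |
| Follow-up | 3 months or 1 year (2.2) | 6 weeks on treatment (2.3) |
| Dose | 20 mg nonelderly, 15 mg elderly in the result cited in 2.7 | Flexible 10-20 mg (2.3, 2.5) |
| Questioning | Not described, except that some events were pre-specified (2.5) | Open question plus prompted list (2.5) |

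These differences need not act in the same direction. Shorter follow-up tends to lower a crude frequency; prompting raises it if the external trials did not prompt. The net direction is unknown.

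**2. What the concurrent arm shares.** By randomisation and common procedure, the placebo group has the same population, planned duration and questioning. The flowchart in section 2.4 first marks adverse events at Med Week 1 and has no Epworth row, so no pre-treatment reference is scheduled either. Placebo is the only internal reference for symptoms such as fatigue and sleepiness.

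**3. Precision of the within-trial comparison.** Inputs: somnolence p1 = 0.07 and p0 = 0.04 (2.2); 90 recruited, 70 expected to be retained (2.5). The allocation ratio is not stated; 1:1 is assumed, giving n = 45 or 35 per arm.

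Half-width = 1.96 × √{[p1(1−p1) + p0(1−p0)]/n} = 1.96 × √[(0.0651 + 0.0384)/n] = 1.96 × √(0.1035/n).

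- n = 45: 1.96 × 0.0480 = 0.094. Expected cases 3.15 v 1.8. Interval 3 ± 9.4, or −6.4 to +12.4 points.
- n = 35: 1.96 × 0.0544 = 0.107. Expected cases 2.45 v 1.4. Interval 3 ± 10.7, or −7.7 to +13.7 points.

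Two-sided power at 5% = Φ{[0.03√n − 1.96√(2p̄(1−p̄))]/√0.1035}, with p̄ = 0.055 and 2p̄(1−p̄) = 0.10395.

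- n = 45: (0.2012 − 0.6319)/0.3217 = −1.34, power 9.0%.
- n = 35: (0.1775 − 0.6319)/0.3217 = −1.41, power 7.9%.

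Power of 80% for 7% v 4% would need about 906 per arm. With 4% on placebo, the smallest suvorexant rate detectable with 80% power is about 24% (n = 45) or 28% (n = 35).

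**4. Noise in the external contrast.** Suppose the two sources were identical and the true suvorexant rate were 7%. The chance of observing more than 7% is P(X ≥ 4) = 0.39 with 45 treated and P(X ≥ 3) = 0.45 with 35. An observed 3 of 45 (6.7%) has an exact 95% interval of 1.4% to 18.3%. The external contrast is therefore imprecise as well as exposed to bias.

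**The case against.** The strongest reply is that this is an unwritten line and not a wrong choice. The plan calls the external contrast descriptive, leaves 2c out of formal testing, and elsewhere describes tolerability as part of a placebo-controlled evaluation. A table by arm fits its wording. This stands, and it rules out some stronger readings:

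- A reader might infer that the external data replace the placebo comparison. The text does not say so; it is silent on by-arm reporting and does not exclude it.
- A reader might infer that any excess over the external rates will be attributed to suvorexant. No sentence does this; the supportable statement is that it could be read that way.
- A reader might infer that prompting must inflate the rates relative to the earlier trials. The documents do not say how those trials elicited events. The list here is drawn from them, and part of it was pre-specified there. Ascertainment is a possible difference, not an established one.
- A reader might want a figure for the bias. The documents give no background rate for this population, so any multiple would only restate an assumption.

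A second reply is that the within-trial comparison is too imprecise to help: two or three cases against one or two. The imprecision is real, and it argues against a powered test. It does not favour the external contrast, which is also noisy and has confounding that a larger sample would not remove.

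**Conclusion.** The concern holds in a limited form. The external suvorexant data are the only comparator section 2.7 names for adverse events, no within-trial comparator is stated, and 2c has no analysis, although the design supplies a randomised control. A difference from the external rates could not be separated from the documented differences in population, dosing and follow-up, or from ascertainment if that differed.

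The size of any resulting bias cannot be given from the documents. What can be given is the precision of the alternative: a half-width of about 9.4 points with 45 per arm and 10.7 with 35, and two-sided power of about 8-9%. These figures assume 1:1 allocation, the 7% and 4% rates of section 2.2, and a normal approximation that is rough at such small counts. The change is worth making because it uses data already collected, but it will not establish tolerability by showing no difference.

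**What to change.** Add to section 2.7, in substance:

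> Tolerability (hypothesis 2c) will be summarised primarily as suvorexant versus concurrent placebo: for each queried event, the count and percentage per arm, the risk difference and its 95% confidence interval; the same for discontinuation because of adverse events; and Epworth scores by arm with the difference and 95% confidence interval. The contrast with earlier suvorexant trials is secondary context; population, dosing, length of exposure and possibly ascertainment differ.

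State which participants form the denominator, and use an interval suited to small counts, such as a score interval for the risk difference. Add one sentence that the comparison is imprecise at this sample size and that the absence of an observed difference will not be taken as evidence of tolerability. No test or increase in sample size is needed.

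The cost is a short addition to section 2.7 and one table. No new data or visits are required.

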
2.5 Study Procedures
	
Participants
 
Recruitment:
 
We will recruit 90 adults with the expectation of retaining 70 (see power analysis). Participants will be between the ages of 18 to 55 with insomnia and trauma exposure (see below). Recruitment will occur over a 2 1/2 year period with the expectation of recruiting 3 per month and having 2 months for start-up and 6 months for final data analysis and preparing presentations and manuscripts. We will utilize advertisements including 10 radio and 10 newspaper ads in the Washington Post Express at early and other strategic times during study recruitment. We will also continue to employ recruitment methods that have been successful for our program in recruiting participants with trauma-related symptoms including posting flyers on the Howard University campus and in strategic locations in the Washington DC community, and referrals from prior participants. Those who meet initial criteria by phone or on-site screening will be invited to the Clinical Research Unit (CRU) for further screening and informed consent. We will recruit men and women. This study will be open to all ethnic and racial groups; however, with the study location of Howard University in urban DC we anticipate that many of the recruited participants will be from minority groups.
 
Screening Procedures:
 
Participants will initially be screened over the phone with a preliminary checklist of inclusion and exclusion criteria as well as be further informed regarding the purpose and goals for the study. Those who remain interested and appear to meet study criteria will be invited for the screening evaluation at the Howard University CRU. (See study flow chart.)
 
Inclusion criteria and justification:
 
Physically healthy young to middle-aged adults (age 18-55) who report on screening and are confirmed by a clinical interview to meet the Diagnostic and Statistical Manual of Mental Disorders – 5th Edition (DSM-5) criteria for primary insomnia and Criterion A (exposure to a traumatic event) for PTSD.²⁵ Insomnia symptoms must have started or worsened after the exposure to the index trauma. We anticipate that approximately half of the recruited sample will meet criteria for PTSD thus enabling comparisons between those with TRI present or absent PTSD.
 
Exclusion criteria:
 
 1. Psychiatric disorders other than insomnia, PTSD and specific phobias; including bipolar and psychotic disorders and meeting criteria for DSM-5 moderate alcohol or drug use disorders within the past year. 2. Diagnosis of a sleep disorder other than insomnia including PSG findings of apnea/hypopnea or periodic limb movement indices > 10/hour;

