------------------------------------	---

- 3. Consistent (daily) use of medication other than medications taken for blood pressure or nonnarcotic medications for pain and/or inflammation, or medical conditions that compromise sleep;
- 4. Caffeine use exceeding 5 cups of coffee per day or its equivalent;
- 5. Habitual bedtimes after 3AM, habitual rise times after 10AM, or habitual napping > 1hour/day;
- 6. Pregnancy or breastfeeding, or expecting to conceive while in study (sexually active women will be required to use a medically acceptable form of birth control);
- 7. Positive urine toxicology.

Procedures

Medication:

After the baseline screening, participants will be randomly assigned to either the suvorexant or placebo group, and suvorexant or placebo will be administered to be taken one hour before bedtime. Randomization will be stratified for the presence or absence of PTSD (full or subthreshold) and gender. Medication will be managed by the research pharmacy and provided to the participant by CRU nursing staff with instructions for use. In case of a missed appointment they will receive a 15 day supply except for between treatment week 3 and week 6 when they will receive a 4 week supply. Initial dosing will be 10 mg. At week one, [name] or a study clinician in consultation with [name], will determine whether to increase to 20 mg. based on tolerance of the medication and persistence of symptoms. If there are no, or only negligible, side effects and insomnia symptoms remain present then the dose will be increased. If tolerability is compromised by the dose increase the study clinician will have the option of reducing back to 10 mg if done at or before the week 2 study visit. Dose increases can be deferred until week 2 but after this visit medication dose will be held constant until the end of the study. Participants will discontinue medication after the week 6 study visit. At the final follow-up 1 week later clinical assessment will inform the study clinician's recommendation for further treatment including possible resumption or initiation of suvorexant. At each medication study the coordinator or research nurse will conduct a pill count and review diaries to determine adherence. They will also query for potential adverse events including a list of the most common adverse effects reported in the suvorexant trials^{22,23} will be queried as well as any events suggestive of parasomnias or narcolepsy phenomena (see Assessments below).

Assessments:

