
	
minutes), SWS and the duration of continuous segments of REM sleep will increase with suvorexant than placebo: Participants with reduced baseline SWS (below vs. above 100 minutes) and mean REM segment duration (below vs. above 15 minutes) will be included in the analyses. 2 (Group) x 2 (Time: Baseline and Med week 3) mixed ANOVAs or ANCOVAs will be performed to compare treatment changes in SWS and REM segment duration between the suvorexant and placebo groups.
 
Power Considerations:
 
G*Power 3.1 ³³ was used to conduct power analysis.
 
Power analysis for Hypothesis 2a) is based on the effect size estimated using findings of Herring and colleagues' ²² placebo controlled trial of suvorexant in adults with insomnia. Since there are no data for suvorexant on trauma related nightmares and PTSD symptoms, we also used Taylor and colleagues' ²⁴ placebo controlled trial of prazosin in civilian outpatients with PTSD, sleep disturbances, and nightmares. Taylor et al. found a large-size effect of prazosin on changes in trauma-related nightmare severity compared with placebo ($d = 0.96$ or $f = 0.48$) and PTSD severity ($d = 0.79$ or $f = 0.40$) and a medium-size effect on changes in trauma-related insomnia symptoms severity ($d = 0.50$ or $f = .25$). Herring and colleagues found a small-size effect of a 1-month suvorexant treatment (20mg for nonelderly and 15mg for elderly) on insomnia severity measured by the ISI ($d = 0.39$ or $f = 0.20$). To detect an $f = 0.20$ Group x Time interaction effect in the proposed mixed ANOVA with 80% power, a total of 42 participants are needed.
 
Power analysis for Hypothesis 2b) is based on the effect sizes estimated using Krakow and colleagues' findings ³⁴ from their study examining effects of cognitive behavioral therapy for nightmares and insomnia in crime victims with PTSD. They found correlations between changes in nightmare frequency, insomnia severity, and sleep quality and changes in overall PTSD symptom severity ranging from $r = .37$ to $.40$. A sample size of 43 will allow for detecting similar size effects with 80% power.
 
Power analysis for Hypothesis 2d) is based on findings from the aforementioned Herring and colleagues' study. They found that effects of suvorexant on sleep latency and WASO were $f = 0.17$ and 0.31, respectively. To detect an effect size of 0.17 using the proposed mixed ANOVA with 80% power, a total of 70 participants are needed.
 
Power analysis for Exploratory hypothesis 2e) is based on findings from the aforementioned Taylor and colleagues' study. They found that the effect of prazosin on mean REM period duration was $f = 0.50$. Using the proposed mixed ANOVA, a total of 16 participants will allow for detecting a large size within-between interaction effect ($f = 0.50$) with 80% power.

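### Covariates are to be chosen by significance tests of baseline differences rather than pre-specified, so an outcome's baseline value would rarely enter as a covariate and precision is usually lost

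*Combined protocol and SAP*

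**What the plan says.** Section 2.7, under Hypothesis 2a, compares the arms on baseline characteristics with t-tests or chi-square tests and continues: "If a significant group difference is found in some of the variables, the variable(s) will be included in subsequent analyses as a covariate(s". The characteristics are not listed, and no level is given for these tests.

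The outcome models follow from that rule. For 2a: "We will perform 2 (Group) x 3 (Time: baseline, Med week 3, and week 6) mixed ANOVAs or ANCOVAs". For 2d: "We will perform 2 (Group: suvorexant vs. placebo) x 2 (Time: Baseline and Med week 3) mixed ANOVAs or ANCOVAs". In both, the ANCOVA form applies only if the baseline tests have produced a covariate. Hypothesis 2e also offers ANOVA or ANCOVA.

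Section 2.5 (Medication) states: "Randomization will be stratified for the presence or absence of PTSD (full or subthreshold) and gender". Neither factor is named as a model term in section 2.7. The main outcomes there are ISI, CAPS nightmare frequency and total score, and diary and PSG sleep latency and WASO. Hypothesis 2d gives a model for the PSG versions of the last two only.

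**The concern.** A covariate sharpens a treatment comparison because it predicts the outcome, not because the arms happen to differ on it. Among randomised participants, a baseline difference is due to chance. The p-value therefore selects on the wrong property and usually leaves out the most useful covariate, the outcome's own baseline value.

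Two things are at stake. The covariate set for every main outcome is unknown until the data have been seen. And precision available from data already collected is usually lost, including for PSG sleep latency in 2d, the endpoint that sets the sample size: "To detect an effect size of 0.17 using the proposed mixed ANOVA with 80% power, a total of 70 participants are needed".

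A lesser point is that section 2.5 says "We will recruit 90 adults with the expectation of retaining 70 (see power analysis", and the data pre-screening in section 2.7 allows that "any necessary modifications, such as transformation of variables and/or elimination of cases, will be conducted". If the tests are run on the retained set, a difference could also reflect unequal loss, and the p-value would not tell the two apart. The documents do not say which set is tested.

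**Working it through.** **Inputs from the documents.** f = .17 and N = 70 for 2d; f = .20 and N = 42 for 2a; 80% power; alpha .05, stated as one-tailed (all section 2.7); stratification by PTSD and gender (section 2.5).

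**Assumptions.** Equal arms; baseline tests two-sided at .05; the correlation r between baseline and follow-up; and k = follow-up SD / baseline SD. None of these is in the documents.

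**1. Reproducing the plan's sample sizes.** For the Group x Time interaction with m time points, noncentrality is λ = f²·N·m/(1 − r).
- 2d: .17² × 70 × 2 / .5 = 8.092. The F(1, 68) test at .05 has power 80.1%.
- 2a: .20² × 42 × 3 / .5 = 10.08. The F(2, 80) test at .05 has power 80.3%.

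Both planned figures are reproduced at r = .5 with an ordinary F test at .05. At the stated one-tailed .05, the 2d comparison has power 87.9% at N = 70.

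**2. How often a covariate enters.** Under randomisation, a variable with no link to the strata is significant at two-sided .05 in 5% of trials.
- *Baseline value of an outcome:* 4.8% to 4.9% in simulation (N = 70, 20,000 trials per scenario). If PTSD stratum explains part of that value and the arms are balanced within PTSD strata, this falls: 3.8%, 1.9% and 0.5% when the stratum explains 10%, 30% and 50% of the variance. If baseline outcomes are not among the tested variables, it is never.
- *PTSD and gender:* in no simulated trial with blocking within strata, and 4.1% and 4.6% without. The documents do not say whether blocks are used.
- *Any covariate, with 10 tested variables (number assumed):* 33% of null trials with blocking, 39% without.

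**3. Precision lost.** With baseline SD set to 1, the change score has variance 1 + k² − 2rk. Regression on baseline leaves (1 − r²)k². The ratio is

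V = (1 − r²)k² / (1 + k² − 2rk).

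Denominator minus numerator equals (1 − rk)², which is never negative, so V never exceeds 1. It equals 1 only when rk = 1.

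| r | k = .8 | k = 1 | k = 1.2 | k = 1.4 |
|---|---|---|---|---|
| .3 | .50 | .65 | .76 | .84 |
| .5 | .57 | .75 | .87 | .94 |
| .7 | .63 | .85 | .97 | 1.00 |

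**4. Illustration for 2d sleep latency (r = .5, k = 1, V = .75).** Estimating the covariates costs 1 + 1/66 in variance if PTSD and gender are balanced by design, and 1 + 3/64 if not. Residual df are 65.
- Balanced: λ = 8.092/.75/1.0152 = 10.63. Power is 94.3% one-tailed, 89.5% by F test.
- Not balanced: λ = 8.092/.75/1.0469 = 10.31. Power is 93.7% and 88.5%.

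So power moves from 87.9% to about 94% one-tailed, or from 80.1% to about 89% by F test.

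**5. The rule itself, simulated (r = .5, k = 1, blocked, 10 variables, one-tailed).** Power is 87.6% under the planned rule and 94.1% with pre-specified adjustment. Null rejection is 4.6% and 4.9%. The rule recovers almost none of the gain, and it does not inflate type I error.

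**6. Downside.** If V = 1 and all three covariates were useless and unbalanced, λ = 8.092/1.0469 = 7.73 and one-tailed power falls from 87.9% to 86.6%.

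**The case against.** The default analysis already uses baseline. It is a level of Time in every 2a and 2d model, the comparison of changes is valid, and the rule is if anything slightly conservative. A reader might infer that baseline is ignored or that the trial's false-positive rate is at risk. The documents support neither: only entry *as a covariate* is conditional, and the simulated null rejection is below .05.

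The gain in precision rests on r and k, which the documents do not give, and in part of the plausible range it is nil (r = .7, k = 1.4). That stands, and it makes the power gain an illustration rather than an estimate. It does not touch the pre-specification point.

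A reader might also infer that 70 participants is a conservative number once baseline is adjusted for. That is not supported, because the power levels inherit the plan's reading of f. Section 2.7 equates d = 0.39 with f = 0.20. If f = .17 is read the same way, as a .34 SD difference at week 3 with r = .5 and k = 1, then λ = .34² × 70/4 = 2.02. One-tailed power is then about 41% by change score and about 49% adjusted (λ = 2.02/.75/1.0152 = 2.65). The relative reduction in variance is the same under either reading; the absolute levels are not.

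Finally, no gain should be credited to PTSD or gender themselves, since the documents do not say how strongly they predict outcome. They belong in the model because randomisation is stratified on them.

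**Conclusion.** The concern holds as one of precision and pre-specification. The covariates for every main outcome depend on tests that, under randomisation, pick up chance imbalance. The outcome's baseline value would enter as a covariate in about 5% of trials (if tested at two-sided .05; never, if not tested), and the stratification factors rarely or never. The default change comparison remains valid.

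The variance ratio from baseline adjustment never exceeds 1: it is .65, .75 and .85 at r = .3, .5 and .7 with k = 1, and about 1.00 at r = .7, k = 1.4. For 2d sleep latency this is about 6 power points one-tailed or 9 by F test at r = .5, k = 1, in the plan's own convention. These are not independent estimates of the trial's power. The change is worth making: at r = .5, k = 1 the gain is several power points, against a worst-case loss of about one.

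**What to change.** In section 2.7:

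- Delete the baseline significance tests as a rule for choosing covariates, and present the baseline table descriptively.
- For each main outcome (ISI, CAPS nightmare frequency and total score, diary and PSG sleep latency and WASO), pre-specify a model of the post-baseline value or values on treatment, the baseline value of that outcome, PTSD stratum (full or subthreshold versus absent) and gender.
- For PSG outcomes, this is a single model of the week 3 value. For outcomes measured at weeks 3 and 6, use a repeated-measures model that adds visit, treatment by visit and baseline by visit.
- For 2e, adjust for the baseline value only. The subset sizes are not stated and may be small; one covariate costs a factor of 1 + 1/(n − 4) in variance, about 8% at 16 participants and 3% at 35.

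Do not add a statement that the sample sizes are conservative. Which of weeks 3 and 6 takes priority, and how a one-tailed alpha applies to the 2-df interaction test, are separate questions that this change need not settle.

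The cost is wording only, since all covariates are already collected. In 2d it uses three degrees of freedom (68 to 65) and, if all three covariates were useless, about 5% more variance.
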